1.3 Possible risks

Adverse reactions of vitamin K1: occasionally allergic reactions. Mainly occurs when the intravenous injection is too fast, more than 5mg/ minutes can cause facial flushing, sweating, bronchospasm, tachycardia,

hypotension, etc., serious allergic reactions may endanger life. Intramuscular injection can cause redness and swelling. The newborn may suffer from hyperbilirubinemia, jaundice and hemolytic anemia after the use of the product.

.1.4. Benefits

Cerebral hemorrhage is a common disease in Department of neurosurgery. It is an important measure to reduce the mortality and disability rate in the acute stage. Vitamin K1 may reduce the risk of rebleeding in patients with intracerebral hemorrhage, and the amount of brain bleeding is directly related to prognosis. Effectively reduce the amount of intracerebral hemorrhage, improve the prognosis, reduce the length of stay, reduce the time of admission to ICU and reduce the mortality.

2 Test purpose

The effectiveness and safety of vitamin K1 were mainly targeted at patients with cerebral hemorrhage (non aneurysm or vascular malformations, rupture, bleeding). To observe whether vitamin K1 can effectively avoid the increase of cerebral hemorrhage and improve the prognosis.

3 Test design

The study included spontaneous hypertensive intracerebral hemorrhage at super tentorium of cerebellum patients as the research object, to exclude cerebral aneurysms or cerebral hemorrhage, venous malformation of abnormal liver function, taking anticoagulants or antiplatelet drugs in patients. The study was divided into the experimental group and the control group, and a multicenter randomized controlled trial was conducted. In the use of a etamsylate intravenous infusion of 0.5g of patients admitted to hospital within 8 hours later, the experimental group in the incidence of cerebral hemorrhage within 2 days after the daily intravenous infusion of vitamin K1 20mg, the control group received intravenous saline, all patients were no longer use other hemostatic agents. The efficacy and safety of vitamin K1 in the early onset of cerebral hemorrhage were assessed by the observation between two groups.

A randomized, single blind, positive / placebo parallel control, multicenter, clinical trial design was used. The treatment lasted for 2 days and followed up for 6 months.

4 Subjects recruited and exited

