6.1 Experimental medication

6.1.1 Drug delivery

Test drug: vitamin K1 for injection, specification: 10mg each

Contrast drug: normal saline.

All trials were administered by the investigators in a single blind manner,.

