6.1.4 Route of administration

Basic treatment: all subjects according to the routine treatment of cerebral hemorrhage, the use of Phenol ethylamine intravenous 0.5g within 8 hours after admission, another program in accordance with the "Neurosurgery of Wang Zhongcheng", including the surgical removal of hematoma and drainage, conservative treatment, control of intracranial pressure, prevention of complications.

Test group:

Normal saline 100ml+Vitamin K1 20mg, Once a day, intravenous drip, two days in

hospital.

Control group:

Normal saline 102ml, Once a day, intravenous drip, two days in hospital.

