7.5 Concomitant medication and treatment

7.5.1 Basic treatment

Allow the cerebral hemorrhage treated with conventional therapy control of intracranial hypertension, prevention of complications, but it must be the case report form to record the medicine general or other treatment, dosage, reason, use frequency and time etc, so as to summarize, analyze and report.

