7.5.3 Medication and treatment are permitted

(1) The other combined diseases without affecting the curative effect and safety evaluation, can be symptomatic medication, but it must be the case report form to record the medicine general or other treatment, dosage, reason, use frequency and time etc, so as to summarize, analyze and report.

⁽²⁾The follow-up period can use cognitive rehabilitation methods, including occupational therapy, implicit memory rehabilitation, errorless learning, cognitive neuropsychological rehabilitation, rehabilitation and computer assisted cognitive rehabilitation, virtual remote control via the Internet, and the electromagnetic stimulation, should be recorded in detail in CRF.

⁽³⁾The combination drugs used for adverse events during the trial should be recorded in CRF.

8 Therapeutic evaluation standard

Main outcome measures: the amount of intracerebral hemorrhage (0d, 1D, 3D, 7D) at each time after the onset of disease.

Main outcome measures: (1) the amount of the time changes in blood coagulation, platelet levels and GCS scores after the onset (0d, 1D, 3D, 7D); (2) days in ICU; (3) the total hospitalization days; (4) complications including neurological complications, complications, blood coagulation circulatory complications after cerebral hemorrhage; (5) 1m and 6m mRS score.

9 Safety evaluation

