Statistical analysis plan

1. Statistical software

Using STATA version 12.0 statistical software.

2. Special data processing

(1) Missing data: When a certain important data due to loss, miss follow-up, examination is happen, the LOCF method will be adopted to carry out the data and the secondary index will not be transferred.

(2) Outlier data: According to statistical and medical analysis, determine these data will be included or not. Sensitivity analysis was conducted for the outliers of the main targets, including two results consistent with those who did not outliers.

3. Selection of inspection level α and power of test β

(1) Difference test: With $\alpha = 0.05$ as the test standard, two-sided test was adopted, and the statistical methods, statistics and specific P values were given. $P \leq 0.05$ was considered statistically significant.

(2) Superiority test: Based on a power of 80% ($\beta = 0.2$), $\alpha = 0.025$ was conducted for the one-sided test. The difference between the groups and the 95% confidence interval of the mRS score difference to the baseline values after treatment in the experimental group and the placebo group was calculated by the least square method. If the 95% confidence interval between the two groups was greater than 0, the experimental group can be thought to be superior to the placebo group, otherwise not.

4. Statistical expression

(1) The statistical report mainly expressed in form, which was self-evident. It had the title, the heading and the number of cases, the necessary remarks and the text of statistical results and the description of data results.

(2) Descriptive statistics: The measurement data is described by mean number, standard deviation, maximum value, minimum value, 95% confidence interval, median, Q1 and Q3. The enumeration data is described by frequency (constituent

ratio), and corresponding statistics and P value are calculated.

(3) Inferential statistics: Measurement data were compared between groups by analysis of variance or K-W rank-sum test according to the distribution pattern. Enumeration data were compared between groups by R*C Chi-squared test and Fisher exact test. The ranked data was tested by CMH. The main/important therapeutic effect index will use the baseline for the covariant, considering center, operation or not after injury for analysis of covariance.

5. Specific statistical analysis content

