(1) Analysis of program implementation: a list was adopted to summarize the entry and completion of all and each central cases, and tabulate details and the data collation of those cases which are not meet the inclusion criteria, fall off, low compliance, against therapy and drug combination, interview time beyond window.

(2) Analysis the patient compliance and the drug combination during the trail.

(3) Condition of each analysis data set: Based on the analysis of the implementation of the program, determining the data imputation of each deviated test programme case. Summarize the cases of each analysis data sets, such as per-protocol set (PPS), full analysis set (FAS), safety set (SS).

(4) Baseline equalization analysis: Compare the baseline data of demographic data, vital signs and medical history related features.

(5) Analysis of curative effect index :

1) Compare the changes of mRS score to the baseline after using the drug in 2 days, followed up with 1 month and 6 months in the two groups. The main/important therapeutic effect index will use the baseline for the covariant, considering center, operation or not after injury for analysis of covariance. The covariance analysis was performed on the change of mRS score at baseline after 6 months of follow-up. The difference between the groups and the 95% confidence interval of the mRS score difference to the baseline values after treatment in the experimental group and the placebo group was calculated by the least square method. If the 95% confidence interval between the two groups was greater than 0, the experimental group can be

thought to be superior to the placebo group, otherwise not.

2) Compare the changes of cerebral hemorrhage amount to the baseline in the two groups.

3) Compare the changes of coagulation function, platelet level and GCS score to the baseline in the two groups.

4) Compare the number of days stayed in the ICU and the hospital in the two groups.

(6) Safety analysis:

Compare the incidence and classification rate of complications, adverse events and adverse reactions during the test in the two groups, and list the details of each adverse event, such as the detailed occurrence, outcome and the relationship with drugs.

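### The haemorrhage-volume comparison has no rule for CTs taken after clot evacuation; the SAP's operation term, if it applies to volume, repairs this only in part

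*SAP*

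**What the plan says.** - **Aim (Protocol 2):** "To observe whether vitamin K1 can effectively avoid the increase of cerebral hemorrhage and improve the prognosis".
- **Outcome (Protocol 8):** the first-listed main outcome is "the amount of intracerebral hemorrhage (0d, 1D, 3D, 7D) at each time after the onset of disease".
- **Surgery (Protocol 6.1.4):** basic treatment for all subjects follows a textbook, "including the surgical removal of hematoma and drainage, conservative treatment". No surgery rate or timing is given. The exclusion, rejection and exit criteria (4.3 to 4.5) do not mention surgery.
- **Volume analysis (SAP 5(5)2):** "Compare the changes of cerebral hemorrhage amount to the baseline in the two groups". No model and no scan rule follow.
- **General rule (SAP 4(3)):** "The main/important therapeutic effect index will use the baseline for the covariant, considering center, operation or not after injury for analysis of covariance". SAP 5(5)1) repeats this under mRS, and the only analysis it names there for the ANCOVA is 6-month mRS change. Other measurement data go to ANOVA or a K-W rank-sum test.
- **Missing data (SAP 2(1)):** LOCF for important data; secondary indices are not carried forward.
- **Blinding:** Protocol 3 states "A randomized, single blind, positive / placebo parallel control, multicenter, clinical trial design was used", and 6.1.1 states "All trials were administered by the investigators in a single blind manner". Neither says whether those who decide on surgery are blinded.

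**The concern.** The endpoint is meant to show whether K1 limits bleeding into the clot. A CT after evacuation shows what the surgeon left behind. Take an assumed patient with 30 ml at baseline who grows by 6 ml and has 80% removed. The CT then reads 36 x 0.2 = 7.2 ml, a recorded change of 7.2 - 30 = -22.8 ml where the bleeding outcome was +6 ml.

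Two things are at stake. If K1 works, operated patients lose most of the treatment difference and add noise, so the effect is diluted. If surgery is used more in one arm, that arm appears to shrink more, whichever arm it is. The operation term helps, but an operation can follow randomisation and depend on growth, so conditioning on it is not neutral. The same term sits in the mRS model.

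**Working it through.** **Inputs from the documents.** Baseline volume 10-45 ml (Protocol 4.2); two-sided alpha 0.05 (SAP 3(1)). There is no sample size, SD, effect size, surgery rate or timing, so there is no plan figure to reproduce. Everything below is assumed and illustrative. Surgery rates are control v K1; differences are K1 minus control.

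**1. Dilution by hand.** If a share p of each arm is operated on regardless of volume and a fraction r of the clot is left, the effect becomes delta x (1 - p x (1 - r)). With delta = 3 ml, r = 0.2 and p = 0.2: 3 x (1 - 0.2 x 0.8) = 2.52 ml. For p = 10/20/30/40% it is 2.76/2.52/2.28/2.04 ml. Evacuation also adds variance. Simulated at 112 per arm (SD of growth 8 ml, 80% power without surgery, 70-90% of the clot removed), power falls to 48/31/23/19% unadjusted and 74/63/58/53% with the operation term.

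**2. False effect by hand.** Difference = (surgery rate in K1 - rate in control) x mean volume removed. With 24 ml removed (0.8 x 30) and 20 v 30% surgery: (0.30 - 0.20) x 24 = 2.4 ml of apparent benefit. Reverse the rates and it is apparent harm of the same size.

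**3. Simulation with surgery driven by volume.** Baseline uniform 10-45 ml; growth gamma (shape 0.7); logit P(operation) = a + (baseline + growth - 35)/10, with a set per arm to give the stated rate; 50-80% of the clot removed. Mean growth is 8 v 4 ml in the first three rows (true effect -4.0 ml) and 6 v 6 ml in the last.

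| True effect | Surgery | No operation term | With operation term |
|---|---|---|---|
| -4.0 ml | 10 v 6% | -2.6 to -1.8 ml | -3.3 to -3.0 ml |
| -4.0 ml | 20 v 14% | -2.0 to -0.9 ml | -3.0 to -2.6 ml |
| -4.0 ml | 40 v 33% | -1.6 to -0.05 ml | -2.6 to -1.9 ml |
| 0 | 20 v 30% | -1.9 to -3.1 ml | -0.3 to -0.4 ml |

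Rejection rates at 100 per arm:
- No effect, 20 v 30% surgery: about 32-37% by ANOVA, 27-30% by K-W, 6-8% with the operation term.
- No effect, equal surgery: 4-6%.
- True effect, 10 v 6% surgery: K-W power 52-64%, against 94-96% with the operation term.

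**4. What the operation term leaves.** In the step 1 model with no drug effect and 112 per arm, let the threshold for operating differ by arm. If it is a volume threshold (17 v 26% operated), the adjusted estimate is -0.5 ml with 8% rejections (15% at 300 per arm). If it is a growth threshold (11 v 23%), it is -1.2 ml with 23% (54% at 300).

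**5. Last CT between first dose and evacuation.** Step 3 model, 100 per arm, when none/half/all of the operated patients have such a CT:

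| No such CT is treated as | True -4.0 ml, 20 v 14%: estimate; power | No effect, 20 v 30%: bias; rejection |
|---|---|---|
| Missing | -2.62/-3.39/-3.99 ml; 86/94/98% | -0.30/-0.10/-0.01 ml; 5.7/4.2/5.2% |
| Zero change (D0 carried forward) | -1.90/-2.94/-3.99 ml; 70/89/98% | -0.68/-0.36/-0.01 ml; 15.8/6.1/5.2% |

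The operation-adjusted ANCOVA has 87-94% power in the first of these settings. The rule therefore gains only where such CTs exist, and treating the change as missing is better than LOCF.

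**6. mRS.** In one assumed model (no growth effect, 20 v 30% surgery, surgery without benefit) the total difference is 0.00 and the operation-adjusted one -0.05, with 4.7% v 6.4% rejections.

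**The case against.** The strongest reply is that the SAP already deals with surgery. Protocol 8 calls volume a main outcome, SAP 4(3) applies ANCOVA with an operation term to main indices, and under that term the false effect nearly disappears. This stands in large part. A reader might infer that the plan ignores surgery and will produce false positives; the documents do not support that. A false effect needs surgery that differs by arm. The single-blind design leaves this possible, but nothing shows that it will happen, and the textbook the protocol cites may set one criterion for both arms.

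It does not close the point. The term does not remove attenuation. It leaves bias when surgery depends on growth and differs by arm. SAP 5(5) repeats it under mRS only, so its application to volume is an inference.

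A second reply is that the SAP never says evacuated volumes count as shrinkage. That is right: the defect is an unstated rule. But a post-evacuation CT is an observed value, and a comparison of change from baseline without exception includes it. LOCF does not remove it, and would carry an evacuated volume forward if a later CT were missing.

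A third reply is that the remedy may gain little, and step 5 confirms this where no CT lies between dose and operation. CT timing is itself unclear. Protocol 8 lists day 1. The CT row of the flow chart (Protocol 7.5) appears to have no day-1 mark, but that table is damaged in the text available, so this is something to check and not a finding.

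**Conclusion.** The point holds, and the SAP should be changed. The volume comparison lacks a rule for scans after evacuation, and as written those scans enter as shrinkage.

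- **If SAP 4(3) covers volume (likelier):** the main cost is attenuation, a true -4.0 ml read as about -3.3 to -1.9 ml in the model. The false effect at 20 v 30% surgery is small (-0.3 to -0.4 ml), but larger if growth itself triggers surgery differently by arm.
- **If it does not:** the ANOVA or K-W test is diluted and can show a false effect in either direction, with about 27-37% false significance at 100 per arm and 20 v 30% surgery.

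It would go too far to say that type I error is inflated in general: with equal surgery and no K1 effect it stays near 5%. The mechanism follows from the documents. Every size rests on assumed surgery rates, growth, fraction removed and sample size. The effect of the operation term on mRS is unknown and probably small.

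**What to change.** 1. **SAP 5(5)2) and 2(1):** state that volumes measured after evacuation are not counted as haematoma change. Use the last CT after the first dose and before evacuation. Where none exists, treat the change as missing, neither zero by LOCF nor an evacuated volume carried forward. Report the operation-adjusted ANCOVA and the all-scans analysis as sensitivity analyses. Say that the rule's advantage depends on how many operated patients have such a CT, and reconcile the CT days in Protocol 7.5 and 8. No composite endpoint is needed.
2. **SAP 4(3) and 5(5)1):** state whether the ANCOVA covers volume. Limit primary-model covariates, including for mRS, to baseline value, centre and operation before randomisation. Put later operations in a sensitivity analysis only.
3. **Reporting:** give surgery rate and timing by arm.

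The cost is SAP wording and at most one CRF field. Protocol 7.5.1 already asks the CRF to "record the medicine general or other treatment, dosage, reason, use frequency and time etc"; confirm that this captures the date and time of operation. No extra scan or patient is asked for, and no rule on when to operate is proposed. The downside is lost information for operated patients without a CT between dose and operation; for them the result stays attenuated. Bleeding after surgery falls outside the measure and should be reported separately.

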9.6 Adverse events and test drug evaluation

According to the sequence between the occurrences of adverse drug evens and usage of drugs, the type of drug reaction after drug withdrawal reaction is reduced, will disappear or reappear, causality assessment of adverse events related to study drug is certainly relevant, probably, may be related, and certainly can not. The first three were considered to be relevant to the study of the drug, which was evaluated as untoward effect of drug.(ADR).

Adverse events associated with the study of drugs are as follows:

(1)Affirmation: the use of evidence for the study of drugs, the occurrence of adverse events and research, the use of drugs have a reasonable chronological order, adverse events to study drug interpretation, more reasonable than other explanations. The drug withdrawal reaction is positive, and the repeated use (if feasible) is positive.

⁽²⁾Likely related: evidence of the use of research drugs, occurrence of adverse events, and rational timing of drug use in the study. Adverse events are more reasonable in explaining drug explanations than in other explanations. Positive drug withdrawal reaction.

It may be related to the evidence of the use of research drugs, the occurrence and use of adverse events, and the timing of the study of drugs. Adverse events can also be explained by other reasons. Positive drug withdrawal reaction.

③ Perhaps irrelevant: the use of evidence for the study of drugs, the occurrence of adverse events, explained by other reasons is more reasonable. Withdrawal reactions were negative or unclear. (4) Absolutely unrelated: no use of research drugs, or the use of research drugs and adverse events unrelated to the time, or otherwise clearly lead to adverse events.

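### The between-arm test of adverse reactions can be biased against vitamin K1, because the causality rule can be read to leave saline patients no route to a reaction and blinded rating is not stated

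*SAP*

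**What the plan says.** SAP 5(6) sets out the safety analysis: "Compare the incidence and classification rate of complications, adverse events and adverse reactions during the test in the two groups". It also asks for a listing of every event with its relationship to the drug.

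The method for counts is in SAP 4(3): "Enumeration data were compared between groups by R*C Chi-squared test and Fisher exact test". The SAP does not say which of the two tests applies when. SAP 3(1) sets the level at 0.05, states that a "two-sided test was adopted", and counts P at or below 0.05 as significant. Together these give a planned two-sided test of adverse reactions between the arms.

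Protocol 9.6 decides which events count as reactions. The three upper causality classes (certain, likely, possible) make an event an adverse drug reaction. The definition of each begins from evidence that the research drug was used. The bottom class begins: "Absolutely unrelated: no use of research drugs".

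Protocol 6.1.1 states "Test drug: vitamin K1 for injection, specification: 10mg each" and names saline separately as the contrast drug. On masking it says "All trials were administered by the investigators in a single blind manner", without saying who is blind. Section 9.3.1 gives the first causality assessment to the research physician.

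**The concern.** A between-arm test is informative only if the outcome can be recorded in both arms by the same rule. All adverse events and complications meet that condition. Adverse reactions may not.

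If the research drug in 9.6 means vitamin K1, a saline patient has not used it, and any event in that patient falls into the bottom class. If saline does count, a rater who knows the arm has little reason to attribute an event to it. In both cases the outcome depends partly on treatment arm. The possible class also admits events that have another explanation, so a non-causal event can become a reaction under vitamin K1 while the same event under saline does not.

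Safety is one of the trial's stated purposes in Protocol section 2. A small P value for adverse reactions would be read as an effect of the drug when it might reflect labelling alone.

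**Working it through.** The documents state no sample size and no adverse event or reaction rate, so there is no planned figure to reproduce. The 80% power in SAP 3(2) concerns the mRS test.

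**Inputs from the documents.** Fisher's exact or chi-squared test, two-sided, significant at P ≤ 0.05 (SAP 3(1), 4(3)).

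**Assumptions.** Equal arms of n = 50, 100 or 200. A share q of K1 patients, from 1% to 10%, has a non-causal event that is rated related. Saline is held at 0. Vitamin K1 causes no reactions.

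**Step 1: how many reactions against 0 are significant?**

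- Fisher, two-sided, x against 0 in equal arms: P = 2 × C(n, x) / C(2n, x). At n = 100 and x = 6, P = 2 × (100/200) × (99/199) × (98/198) × (97/197) × (96/196) × (95/195) = 0.029. At x = 5, P = 0.059. So 6 against 0 is needed.
- Uncorrected chi-squared: χ² = 2nx / (2n − x). At n = 100 and x = 4, χ² = 800/196 = 4.08 and P = 0.043. At x = 3, χ² = 600/197 = 3.05 and P = 0.081. So 4 against 0 is needed.

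Both thresholds were the same at every size checked (30, 50, 100, 200 and 500 per arm).

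**Step 2: chance of a significant false excess.** This is P(X ≥ 6) for Fisher or P(X ≥ 4) for chi-squared, with X ~ Binomial(n, q). For n = 100 and q = 5%, Fisher gives 1 − P(X ≤ 5) = 1 − 0.616 = 0.384, and chi-squared gives 1 − P(X ≤ 3) = 1 − 0.258 = 0.742.

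| n per arm | q | Fisher | Chi-squared |
|---|---|---|---|
| 50 | 1% | 0.0% | 0.2% |
| 50 | 5% | 3.8% | 24.0% |
| 50 | 10% | 38.4% | 75.0% |
| 100 | 1% | 0.1% | 1.8% |
| 100 | 5% | 38.4% | 74.2% |
| 100 | 10% | 94.2% | 99.2% |
| 200 | 1% | 1.6% | 14.2% |
| 200 | 5% | 93.8% | 99.1% |
| 200 | 10% | about 100% | about 100% |

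**Step 3: the same events rated alike in both arms.** With the same q in each arm and no true effect, the chance of a significant K1 excess (exact enumeration) is at most 1.7% by Fisher and 2.6% by chi-squared over this grid. At n = 100 and q = 5% it is 1.0% and 2.2%. The inflation in Step 2 therefore comes from unequal rating.

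**Step 4: is an exact zero needed?** No. If 1% of saline patients and 8% of K1 patients are rated as having a reaction, again with no true effect, Fisher gives a false excess in 57% of trials at 100 per arm and 81% at 150.

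**The case against.** A reader might infer more: that a saline patient cannot have an adverse reaction, that the test is therefore against a fixed zero, and that a false excess will appear. The documents do not support that, for four reasons.

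- **The term is undefined.** Section 9.6 never says what counts as a research drug. Saline is listed in 6.1 under the heading for experimental medication, 9.1 ties a reaction to prescribed drugs in general, and 6.1.4 gives both arms another active hemostatic agent. The exclusion of saline is one reading, though a natural one, because the heading of 9.6 refers to the test drug.
- **The blinded party is not named.** Section 9.3.1 mentions an emergency envelope, if applicable, which would serve little purpose if every treating physician knew the arm. This leaves the matter open and does not establish blinded rating.
- **An excess is not certain.** Even the possible class in 9.6 requires a positive withdrawal reaction, and negative or unclear withdrawal goes to a class that does not count as a reaction. This may keep q low. By Fisher, six such patients are needed. Some reactions under vitamin K1 may also be real, so an observed excess need not be false.
- **The main safety comparison is intact.** The same SAP sentence compares all adverse events and complications, which do not depend on attribution. No decision rule uses the adverse reaction P value, and the suspension criteria in Protocol section 5 do not refer to it.

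All four stand. They limit the claim to a possible bias in one of three parallel safety comparisons. They do not remove it, because nothing in the documents ensures that both arms are rated by the same rule.

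**Conclusion.** The point holds as a minor one. SAP 5(6) tests an outcome that 9.6 can be read to deny to saline patients, and nothing shows that causality is rated blind to arm. The test can therefore be biased against vitamin K1.

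The size cannot be fixed from the documents. Over the assumed sizes and shares, the chance of a significant false excess runs from about 0% to nearly 100%. It is negligible at a 1% share with 100 or fewer per arm under Fisher, and substantial at 5% with 100 or more per arm. Leaving the choice between Fisher and chi-squared open widens the range further.

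These figures assume saline held at 0 and no true reactions to vitamin K1. They show what the rule would permit and do not forecast this trial's result.

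**What to change.** 1. In Protocol 9.6, define exposure as the assigned study infusion, vitamin K1 or saline, so that both arms are rated by the same rule. State also whether the rater is blind to arm.
2. In SAP 5(6), rest the between-arm tests on all adverse events, serious adverse events and complications, regardless of causality.
3. Present adverse drug reactions by arm descriptively, without a P value. The listing already planned in SAP 5(6) can carry the detail.

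The first change alone removes the structural zero. It does not stop a rater who knows the arm from attributing events unequally, which is why the second and third are also needed.

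The cost is a few words in each document and the loss of the adverse reaction P value. No new data are needed, and clinical management does not change.

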6.1.5 Test cycle

Medication for 2 days + followed up for 6 months.

7 Test procedure and plan

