9.3.2 Record of adverse events

(1) A physician should perform a record of adverse events, including at least the description of the adverse events, the time of occurrence, the length of the termination, the frequency of attack, and the need for treatment and, if necessary, records of the treatment given.

② In the original record as far as possible with the occurrence and development of SAE records, after the treatment, and record in the CRF table, the SAE track, until we get a proper solution or stable disease or a clear reason to research, clinical drug research institutions ethics committee, unit state food and drug administration, etc. provide a final report.

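### SAP 5(6) compares safety events only over the whole test, which dilutes an adverse-event excess tied to the 2-day exposure; an early-onset comparison by event type should be added

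*SAP*

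**What the plan says.** SAP 5(6) gives the between-group safety comparison in one sentence: "Compare the incidence and classification rate of complications, adverse events and adverse reactions during the test in the two groups". The sentence goes on to "list the details of each adverse event, such as the detailed occurrence, outcome and the relationship with drugs". The only period it names is the test itself.

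Protocol 6.1.5 defines that period: "Medication for 2 days + followed up for 6 months". The flow chart in 7.5 charts complications and adverse reactions from D0 through the month-6 visit. Neither document defines a dosing-period or early-onset window for safety.

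Other relevant text:

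- Protocol 1.3, on allergic reactions to vitamin K1: "Mainly occurs when the intravenous injection is too fast, more than 5mg/ minutes can cause facial flushing, sweating, bronchospasm, tachycardia". It also names hypotension and life-threatening allergic reactions.
- Protocol 1.1.1 names thrombosis as a possible price of controlling the bleeding.
- Protocol 9.6 defines an adverse reaction through causality categories: "The first three were considered to be relevant to the study of the drug".
- Protocol 9.3.2 requires each record to hold "the description of the adverse events, the time of occurrence, the length of the termination", so onset time is collected.
- Protocol 6.1.1 says the investigators give the drug in a single-blind manner.

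**The concern.** Safety is half of the stated purpose in protocol section 2. The reactions named in 1.3 are tied to intravenous administration, which lasts 2 days. These are patients with acute cerebral haemorrhage, and routine care under 6.1.4 includes surgical removal of haematoma and drainage. Many will have some adverse event within 6 months whichever arm they are in. A patient who would have had an event anyway cannot add to the difference in the proportion with at least one event, so that difference shrinks as background accumulates. A finding of no difference on the overall row would then say little about the infusions.

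The SAP's classification rate is not defined. It could mean type, severity grade or causality, but none of these is a split by time.

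**Working it through.** **No figure to reproduce.** The documents state no sample size, event rate or safety power. The test level is in SAP section 3 (two-sided 0.05). Everything else below is assumed: 200 per arm with equal allocation, acute reactions in 2% of controls and 7% on vitamin K1, and background events independent of these reactions and equal in both arms.

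**Formulas.** With acute-reaction risk a and background risk b in a window, the risk of at least one event is p = 1 − (1 − a)(1 − b). The difference between arms is therefore (1 − b) × 5 points. Power = Φ[(d − 1.96 × SE0)/SE1], where SE0 is the pooled and SE1 the unpooled standard error. It counts only results in the direction of harm, so its floor with no effect is 2.5%.

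**One case in full (b = 10%).** Control 1 − 0.98 × 0.90 = 0.118; vitamin K1 1 − 0.93 × 0.90 = 0.163; d = 0.045. SE0 = √(2 × 0.1405 × 0.8595/200) = 0.0348 and SE1 = 0.0347. Power = Φ[(0.045 − 0.0681)/0.0347] = Φ(−0.67) = 25%.

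| Window | Assumed background | Risks | Difference | Power |
|---|---|---|---|---|
| To D7 | 10% | 0.118 v 0.163 | 4.5 points | 25% |
| To D7 | 20% | 0.216 v 0.256 | 4.0 points | 15% |
| To D7 | 30% | 0.314 v 0.349 | 3.5 points | 11% |
| To D7 | 40% | 0.412 v 0.442 | 3.0 points | 9% |
| 6 months | 40% | 0.412 v 0.442 | 3.0 points | 9% |
| 6 months | 60% | 0.608 v 0.628 | 2.0 points | 6% |
| 6 months | 80% | 0.804 v 0.814 | 1.0 point | 4% |

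With acute reactions of 5% v 12%, power is 38%, 24%, 17% and 13% up to D7, and 13%, 8% and 6% over 6 months.

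**A window of only the 2 dosing days.** Assume a 5% excess reaction risk on vitamin K1, none in controls, and a background of 10% in 2 days and 50% in 6 months. The differences are 0.90 × 5 = 4.5 points and 0.50 × 5 = 2.5 points. Power at 200 per arm is 28% against 7%.

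**A specific reaction type that is rare outside the infusion.** A longer window adds almost no background here. With 1% in controls and a 5% excess (1 − 0.99 × 0.95 = 5.95%), Fisher exact power is 31%, 73% and 92% at 100, 200 and 300 per arm.

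**What this shows.** Dilution of the overall row is real. Shortening the window recovers part of the loss, and nothing if the early background is as high as the late one. Separating event types recovers more.

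**The case against.** The strongest objection is that SAP 5(6) does not rest on one pooled rate. It compares complications, adverse events and adverse reactions as three groups, with a classification rate, and lists each event with its occurrence and drug relationship. Under protocol 9.6 the timing of an event relative to dosing is part of the causality assessment, so exposure-linked timing already enters the adverse-reaction row. A reader might infer that infusion reactions are swamped, or that the safety analysis can scarcely show harm. The documents do not support that: it describes the overall row, not the whole of 5(6).

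This stands, but the safeguard is partial. The adverse-reaction row depends on judgement in a single-blind trial whose drug the investigators give, and nothing says the assessor is unaware of the arm. Tachycardia, hypotension and sweating can also come from the haemorrhage, and 9.6 moves events better explained otherwise out of the adverse-reaction count. All three related categories in 9.6 also call for a positive withdrawal reaction, which a thrombosis need not show. The listing involves no comparison between arms, and a window chosen after reading it would be post hoc.

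The objection is also right that judgement bias could run towards over-attribution to vitamin K1, which would not give false reassurance. The direction is unknown. A comparison by onset time needs no attribution at all.

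A second objection is that the early week has its own disease events. That is correct, and it is why the table includes background before D7.

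**Conclusion.** The point holds in a limited form. The only safety period stated is the whole test, so the overall adverse-event comparison dilutes an excess arising in the 2 dosing days, and the other elements of SAP 5(6) offset this only in part.

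Its size cannot be taken from the documents. On the assumed inputs, any-event power is about 25% to 9% up to D7 against 9% to 4% over 6 months. A reader might be tempted to set the 68% power for acute reactions alone (2% v 7%, no background) against those 6-month figures. That is not like for like, because it leaves background out of one side only. The any-event gain is modest and disappears when the two backgrounds are equal; the main gain is from comparing by event type within the early window.

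Nor do the documents support making the early window the main safety comparison at the expense of the longer one. Thrombosis, named in protocol 1.1.1, need not appear before D7. This is a worthwhile addition to the SAP, not a fatal flaw.

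**What to change.** In SAP 5(6), add a prespecified between-group comparison of patients with at least one event whose onset falls (a) in the dosing period and (b) from first infusion up to D7. Tabulate both by event type, including the reactions named in protocol 1.3, as well as overall. State in the same place what classification rate means. Keep the whole-test comparison at equal standing.

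No new data are needed: onset time is recorded under 9.3.2 and D7 is an existing time point in the flow chart. The cost is SAP wording, one more table and some extra comparisons, which raise the chance of an isolated positive result. The event types should therefore be listed before the data are seen.
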